### 2.2 Secondary Objectives

- 2.2.1 To assess the impact of Voxx HPT Socks compared to placebo socks on quality of life in patients with cancer experiencing chemotherapy-induced peripheral neuropathy.
- 2.2.2 To assess the impact of Voxx HPT Socks compared to placebo socks on the experience of cancer-related symptoms in patients with cancer experiencing chemotherapy-induced peripheral neuropathy.

2.2.3 To assess the feasibility of using Voxx HPT Socks to treat chemotherapy-induced peripheral neuropathy in patients with cancer.

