### 2.3.2 Secondary Endpoints

- 2.3.2.1 Impact on chemotherapy-induced peripheral neuropathy will be objectively measured by changes in scores on the Total Neuropathy Scale clinical I(TNSc) and Timed Up and Go (TUG) test.
- 2.3.2.2 Impact on quality of life will be measured by the changes in scores on the Patient-Reported Outcomes Measurement Information System 29 (PROMIS-29).
- 2.3.2.3 Impact on cancer-related symptom experience will be measured by changes in scores on the Edmonton Symptom Assessment Scale (ESAS).
- 2.3.2.4 Feasibility will be measured by the number of hours the socks are worn, as recorded in the patient's daily sock diary.

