### **8.0 STATISTICAL CONSIDERATIONS**

**Sample size and randomization:** This is a pilot crossover study to collect data on effect sizes for the outcomes. Patients will be randomized to one of two treatment sequences as Voxx socks then placebo socks, or placebo socks then Voxx socks. We will enroll 30 patients to allow for dropout to obtain 20 evaluable patients.

**Statistical Methods:** The fundamental analytic approach will be based on a within-subjects comparison of the main outcome measured with Voxx socks versus that measured on placebo in this crossover trial. The primary approach will used linear mixed models with time and treatment effects, adjusted for the repeated measures of subjects nested within sequence in the correlation structure. Carry-over effects will be tested by examining the interaction between treatment and period. In the unlikely event of a statistically significant carry over effect, only data from the first period will be used for the analysis. The overall type I error rate for the primary outcome measure will be controlled at 5%. The main outcome is the score on the Functional Assessment of Cancer Therapy/Gynecologic Oncology Group — Neurotoxicity (FACT/GOG-NTX) Neurotoxicity Subscale.

Data will first be assessed for reliability and general integrity (e.g., distribution characteristics) to ensure that appropriate statistical techniques are applied. Our basic approach to the analysis assumes there are no carry-over effects between the two treatment periods. All subjects entered into the trial will be included in the analysis. Strictly speaking, this is not an "intent-to-treat" policy because the crossover design should assure that each participant receives both Voxx socks as well as placebo in the appropriate treatment periods. If a study participant did not receive one or both treatments, they cannot be included in the primary analysis because that analysis relies on within-subject differences between the treatments. The status of all participants will be reported in the analysis as in the CONSORT recommendations. The fundamental analytic approach will be based on a within-subjects comparison of the relevant outcome measured on Voxx socks versus that measured on placebo. Secondary endpoints will be analyzed the same way as the primary endpoint.

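### The analysis rule for secondary endpoints gives feasibility a Voxx-versus-placebo test, although the feasibility objective names no comparator and its endpoint is hours worn

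*Combined protocol and SAP*

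**What the plan says.** Section 2.2 lists three secondary objectives. Objective 2.2.1 is comparative: "To assess the impact of Voxx HPT Socks compared to placebo socks on quality of life in patients with cancer". Objective 2.2.2, on cancer-related symptoms, has the same comparative form. Objective 2.2.3 does not: "To assess the feasibility of using Voxx HPT Socks to treat chemotherapy-induced peripheral neuropathy in patients with cancer".

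Section 2.3.2 gives the matching endpoints. Those for neuropathy, quality of life and symptoms are changes in scores. The one for feasibility is a quantity of wear: "Feasibility will be measured by the number of hours the socks are worn", taken from the daily diary.

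Section 8.0 then gives a single rule, with no exception for feasibility: "Secondary endpoints will be analyzed the same way as the primary endpoint". The sentence before it describes the approach as a within-subject "comparison of the relevant outcome measured on Voxx socks versus that measured on placebo", and the model is a linear mixed model with time and treatment effects. A 0.05 significance level applies to all secondary objectives.

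Two statements in Section 8.0 bear on who is counted: "All subjects entered into the trial will be included in the analysis", and "If a study participant did not receive one or both treatments, they cannot be included in the primary analysis".

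The same section defines a patient as having completed treatment when the FACT/GOG-NTX was completed at baseline and in both periods and compliance was at least 50% in both periods. Compliance means at least 16 hours of wear per day. No separate feasibility analysis, summary or threshold is given.

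**The concern.** Feasibility asks how much patients wear the Voxx socks. The specified analysis asks whether they wear them more or less than placebo socks. A difference carries no information about the overall level of wear. Followed literally, the plan's feasibility result is a p-value for a sock difference, and a null result could accompany near-continuous wear or very little wear. Similar wear on both socks is plausible, because Section 5.1 makes the placebo socks of the same fabric and identical in appearance.

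The population is a second, smaller matter. If the rule is read to bring the both-treatments exclusion with it, patients who stopped before receiving the second sock would drop out of the feasibility result.

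**Working it through.** There is no power, effect size, SD or feasibility figure in the plan to reproduce. The check sets the text side by side and adds short arithmetic.

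**1. Objective, endpoint and analysis.**

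| Objective | Comparator named | Endpoint | Analysis in Section 8.0 |
|---|---|---|---|
| 2.2.1 quality of life | Placebo | Change in PROMIS-29 | Voxx versus placebo |
| 2.2.2 symptoms | Placebo | Change in ESAS | Voxx versus placebo |
| 2.2.3 feasibility | None | Diary hours worn | Voxx versus placebo |

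Only in the last row does the analysis fail to match the objective. In the time and events table, diary entries fall only in the two wear periods, so hours also have no baseline from which to form a change.

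**2. What a contrast can show.** Let V and P be mean hours per day on Voxx and placebo, and let D = V − P. Adding a common amount c to both gives (V + c) − (P + c) = D. With assumed hours:
- 20 h/day on both socks: 20 − 20 = 0, and the 16 h definition is met every day.
- 6 h/day on both socks: 6 − 6 = 0, and the 16 h definition is never met.

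**3. The same point in a model of the planned type.** One 2×2 crossover data set of 20 patients was simulated with no true sock difference, assuming a between-patient SD of 2 h and a within-patient SD of 1.5 h. The model had period and treatment effects and a random patient effect. Only the overall level of wear was moved.

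| Assumed level (h/day) | Treatment contrast (h) | p | Mean Voxx hours |
|---|---|---|---|
| 6 | −0.605 | 0.109 | 5.63 |
| 12 | −0.605 | 0.109 | 11.63 |
| 16 | −0.605 | 0.109 | 15.63 |
| 20 | −0.605 | 0.109 | 19.63 |

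The contrast and its p-value do not move, while mean Voxx wear rises by 14 h/day (19.63 − 5.63). The absolute values are arbitrary; the invariance is not.

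**4. Population.** The plan enrols 30 to obtain 20 evaluable, an allowance of 30 − 20 = 10. It does not say how many of those would stop before the second sock or how much they would have worn the first. The effect of leaving them out cannot be calculated.

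**5. What a direct summary would deliver.** These figures describe the proposed result and do not measure harm from the current text. The half-width of a 95% CI for a mean is t(0.975, n − 1) × SD / √n: 0.468 SD for n = 20 and 0.373 SD for n = 30. For an assumed SD of 4 h this is 1.87 h and 1.49 h; for 2 to 6 h it runs from 0.94 to 2.81 h (n = 20) and from 0.75 to 2.24 h (n = 30). For missing diaries, suppose 30 patients are dispensed Voxx, 25 diaries are returned and 20 of those patients meet the wear criterion. The proportion is then bounded by 20/30 = 66.7% and (20 + 5)/30 = 83.3%.

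**The case against.** The best reply is that the endpoint is already defined as hours worn, that the mixed model gives a Voxx mean as well as a contrast, and that nothing forbids reporting it. This stands in part. The mean is available, but Section 8.0 does not name it as the feasibility result.

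A second reply is that the plan is not blind to poor wear. The 16 h/day score enters the completion definition, and participant status will be reported along CONSORT lines, so a patient at 6 h/day would not count as having completed treatment. That is true. But that status combines wear with questionnaire completion and requires both periods, so it is not a measure of Voxx wear. A reader might infer that poor wear would go unseen; the documents do not support that.

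Third, the contrast has some relevance. Section 7.2.1 expects foot discomfort and a temporary mild rise in foot pain, and lower wear than on an identical-looking sock would bear on feasibility. This stands, and is a reason to keep the contrast as a supplement.

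Fourth, the both-treatments exclusion is worded for the primary analysis only, with a reason specific to within-subject differences. This also stands. A reader might infer that early stoppers will certainly be dropped and feasibility overstated. Carry-over is only one reading of the rule, and no figure in the documents gives the direction or size of a bias.

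**Conclusion.** The point holds as a mismatch between one secondary objective and its stated analysis. Section 8.0 gives a rule for feasibility, and that rule yields a contrast that cannot separate good wear from poor wear. This follows from the text and from the algebra of a difference; the assumed hours and SDs only illustrate it. The feasibility population also needs to be stated, because Section 8.0 can be read two ways. No bias can be sized from the documents.

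Severity is minor. This is a secondary objective of a pilot, the plan sets no feasibility threshold, the primary endpoint is unaffected, and the diaries that answer the question are already collected. It would be too strong to conclude that the trial cannot assess feasibility.

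**What to change.** Before unblinding (Section 7.5), amend Section 8.0 as follows.

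- Exempt feasibility from the rule for secondary endpoints.
- Name as its result the mean diary hours per day on Voxx with a 95% CI, in all randomised patients dispensed Voxx socks, whether or not they also received placebo. State that the both-treatments exclusion does not apply to it.
- Give the placebo mean and the Voxx-minus-placebo contrast as supplements.
- Report the proportion of these patients who wore Voxx at least 16 h/day on at least 50% of Voxx-period days. Declare this as a Voxx-period adaptation of the completion definition, because the existing 50% has no stated denominator and requires both periods.
- Report how many patients have missing or unreturned Voxx diaries. Give the mean in those with diaries, labelled as such. Bound the proportion by counting missing diaries first as all non-compliant and then as all compliant.

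The cost is wording only; no visit, instrument or patient is added. There are two downsides. The figure may look less favourable than a null difference between socks. And diaries are handed in only at T1 and T2 (Sections 6.2.2 and 6.2.3), so patients lost before T1 may have none, which leaves the proportion as a range.

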### 9.0 STUDY MANAGEMENT

### 9.1 Conflict of Interest

Any reportable conflict of interest will be disclosed to the local IRB and will be outlined in the Informed Consent Form.

### 9.2 Institutional Review Board (IRB) Approval and Consent

It is expected that the IRB will have the proper representation and function in accordance with federally mandated regulations. The IRB should approve the consent form and protocol.

In obtaining and documenting informed consent, the investigator should comply with the applicable regulatory requirement(s), and should adhere to Good Clinical Practice (GCP) and to ethical principles that have their origin in the Declaration of Helsinki.

Before recruitment and enrollment onto this study, the patient will be given a full explanation of the study and will be given the opportunity to review the consent form. Each consent form must include all the relevant elements currently required by the FDA

Regulations and local or state regulations. Once this essential information has been provided to the patient and the investigator is assured that the patient understands the implications of participating in the study, the patient will be asked to give consent to participate in the study by signing an IRB-approved consent form.

Prior to a patient's participation in the trial, the written informed consent form should be signed and personally dated by the patient and by the person who conducted the informed consent discussion.

### 9.3 Registration Procedures

All subjects that sign informed consent will be assigned a subject number sequentially by their date of consent. Those subjects that do not pass the screening phase will be listed as screen failures on the master list of consented subjects. Eligible subjects, as determined by screening procedures and verified by a treating investigator, will be registered on study at Cedars Sinai Medical Center by the Study Coordinator.

Issues that would cause study participation delays after registration should be discussed with the Principal Investigator (PI). If a patient does not begin on-study procedures following registration, the patient's registration on the study may be canceled. The Study Coordinator should be notified of cancellations as soon as possible.

Assignment of Subject ID: The study team will track all subjects who sign consent on a subject screening/enrollment log using a unique ID. Subjects found to be ineligible will be recorded as screen failures. Subjects found to be eligible will be registered using only the three-digit numeric ID assigned at screening that follows the standard SOCCI format.

### A) Eligibility Verification

Prior to registration, subject eligibility must be verified by the Principal Investigator or Treating Investigator and Study Coordinator.

### B) Registration

After eligibility is verified, registration is completed as follows:

- Assign a patient study number
- Enter the patient in OnCore
- Mark the patient as on-study in OnCore

### 9.4 Data Management and Quality Control and Reporting

The data will be entered into a validated database. The study team will manage the database development, data collection, and data entry. The data will be monitored by the study team and the PI. Database lock will occur once quality assurance procedures have been completed.

All procedures for the handling and analysis of data will be conducted using good computing practices meeting FDA guidelines for the handling and analysis of data for clinical trials.

### 9.5 Data and Safety Monitoring

### 9.5.1 Data Monitoring and Quality Assurance

Adherence to the protocol, Good Clinical Practices (GCP), and institutional policy will be monitored by the PI during the course of the study through routine departmental/study staff or Survivorship, Lifestyle, and Supportive Health (SLASH) meetings as applicable. ). In addition, the SOCCI Cancer Clinical Trials Office (CCTO) Quality Management Core (QMC) will conduct a focused internal monitoring visits and audits for data quality and protocol adherence. For any protocol, QMC has the authority to request more frequent reviews or closer safety monitoring if it is deemed appropriate for any reason.

### 9.5.2 Safety Monitoring

As a single-site study, oversight of the progress and safety of the study will be provided by the PI. The PI will maintain continuous safety monitoring for the duration of the study by reviewing subject/study data. Adverse events and unanticipated problems not expected, but if they occur, they will be documented and reported according to CSMC IRB policies and procedures. If the PI becomes aware of any new safety information that may place subjects at increased risk than what was previously known the IRB will be promptly notified and if warranted, enrollment may be held until the PI determines whether a modification to the study is necessary and/or the informed consent documents are updated accordingly.

In addition, this protocol will utilize the SOCCI Data and Safety Monitoring Committee will provide another layer of data and safety oversight. Committee membership includes experts in the field of oncology, nursing, pharmacy, and biostatistics in reviewing the over data, safety, quality, and study integrity of SOCCI interventional IITs. DSMC membership and responsibilities are governed by the committee charter. The DSMC findings and recommendations will be reported in writing to the Principal Investigator. A summary letter will be forwarded by the Principal Investigator or his/her designee to the Cedars-Sinai Medical Center IRB. Refer to the DSMC Charter for details of the DSMC review.

### 9.6 Record Retention

Study documentation includes all Case Report Forms, data correction forms or queries, source documents, and regulatory documents (e.g., protocol and amendments, IRB correspondence and approval, signed patient consent forms).

Source documents include all recordings of observations or notations of clinical activities and all reports and records necessary for the evaluation and reconstruction of the study. Study documents should be kept on file per institutional guidelines.

Government agency regulations and directives require that the study investigator must retain all study documentation pertaining to the conduct of a clinical trial. Study documents should be kept on file until three years after the completion and final study report of this investigational study or as required by institutional guidelines.

### 9.7 Adherence to Protocol

It is the responsibility of the Investigator-sponsor to ensure that patient recruitment and enrollment, treatment, follow-up for toxicities and response, and documentation and reporting at SOCCI are all performed as specified in the protocol. Except for an emergency situation in which proper care for the protection, safety, and well-being of the study patient requires alternative treatment, or a protocol exception request approved by the SOCCI Medical Director and CSMC IRB, the study shall be conducted exactly as described in the approved protocol.

### 9.7.1 Emergency Modifications

Investigators may implement a deviation from, or a change of, the protocol to eliminate an immediate hazard(s) to trial subjects without prior IRB approval. For any such emergency modification implemented, the IRB must be notified as soon as possible, but no more than 10 days from the investigator's awareness of the event.

### 9.7.2 Protocol Exceptions and Eligibility Waivers

An exception is an anticipated or planned deviation from the IRB-approved research protocol, as described in the IRB Policy, Reporting Possible Unanticipated Problems Involving Risks to Subject or Others (UPIRSO) Policy: Institutional Review Board/Research Compliance and Quality Improvement.

A protocol exception most often involves a single subject and is not a permanent revision to the research protocol. Protocol exceptions that extend beyond a single subject should result in a protocol amendment to avoid serial violations.

Planned exceptions to the protocol that are more than logistical in nature and/or impact an eligibility criterion, affect timing of study drug administration, or the investigator assesses the event may impact subject safety and/or study integrity, may not be implemented without prior IRB approval. The PI or her/his designee is responsible for submitting a protocol exception request and its supporting documents to the CSMC IRB if it meets the CS-IRB UPIRSO policy guidelines of a reportable exception/waiver. Study team should also refer to the IRB Reporting Possible Unanticipated Problems Involving Risks to Subject or Others (UPIRSO) Policy: Institutional Review Board/Research Compliance and Quality Improvement guidelines to determine which deviations and exception requests require IRB reporting. Once IRB approved, the deviation or exception can be implemented.

### Special considerations for Eligibility Waivers (EW)

In general, subjects who do not meet the eligibility requirements should not be enrolled. In the rare event that it is appropriate for subject inclusion, the rationale/justification and subject case history should be submitted to the IRB for approval. Such requests for minimal risk studies do not require prior review by the CCTO Medical Director.

### 9.7.3 Other Protocol Deviations

Logistical deviations from the protocol (e.g., minor changes to the study schedule for an individual subject) do not require prior IRB approval unless the deviation has the potential to affect the subject's safety or study integrity. Such planned deviations that do meet this definition and do not affect the subject's safety should be noted in the subject's research record or deviation log as described in the SOCCI CCTO's Standard Operating Procedure 12: Deviation and Noncompliance Reporting.

Unintentional deviations from the protocol that might affect subject safety or study integrity should be reported to the IRB within 10 days from when the investigator becomes aware that such a deviation has occurred, as outlined in the SOCCI Clinical Research Office's Working Instruction 11: Deviation and Noncompliance Reporting. In this case, a Protocol Deviation report must be submitted in CSIRB, per IRB policy, Reporting Possible Unanticipated Problems Involving Risks to Subject or Others (UPIRSO) Policy: Institutional Review Board/Research Compliance and Quality Improvement. All submissions should include a description of the plan to avoid similar

deviations or exceptions in the future.

### 9.7.4 Amendments to the Protocol

Should amendments to the protocol be required, the amendments will be originated and documented by the Principal Investigator. It should also be noted that when an amendment to the protocol substantially alters the study design or the potential risk to the patient, a revised consent form might be required.

The written amendment, and if required the amended consent form, must be sent to the IRB for approval prior to implementation. Repeat exceptions or deviations to the protocol may suggest a protocol amendment is needed.

### 9.8 Obligations of Investigators

The Principal Investigator is responsible for the conduct of the clinical trial at the site in accordance with Title 21 of the Code of Federal Regulations and/or the Declaration of Helsinki. The Principal Investigator is responsible for personally overseeing the treatment of all study patients. The Principal Investigator must assure that all study site personnel, including subinvestigators and other study staff members, adhere to the study protocol and all FDA/GCP/NCI regulations and guidelines regarding clinical trials both during and after study completion.

The Principal Investigator will be responsible for assuring that all the required data will be collected and entered onto the Case Report Forms and/or into a HIPAA-compliant study database. Periodically, monitoring visits will be conducted and the Principal Investigator will provide access to his/her original records to permit verification of proper entry of data. At the completion of the study, all case report forms will be reviewed by the Principal Investigator and will require his/her final signature to verify the accuracy of the data.

